## 2. INTRODUCTION

Interleukin-23 (IL-23) is a disulfide-linked heterodimer of the IL-23p19 and IL-12/23p40 subunits. The receptor for IL-23 comprises the IL-23R and IL-12R subunits (Bloch 2018). IL-23p19 binding to the N-terminal immunoglobulin-like domain of IL-23R is followed by IL-12/23p40 binding to IL-12R $\beta$ 1. Ligand binding leads to phosphorylation and nuclear translocation of STAT proteins.

JNJ-77242113 is a peptide that binds directly to the IL-23R subunit and prevents IL-23 binding, thereby inhibiting proximal IL-23R signaling and downstream effector functions (eg, cytokine secretion). JNJ-77242113 has high potency with an IC50 of ~20 to 30 pM in peripheral human cell based functional assays. Despite its low oral bioavailability (<1%), JNJ-77242113 has demonstrated systemic effects and has provided substantial efficacy in plaque psoriasis clearance in doses 25 mg once daily and greater in the Phase 2b Study, 77242113PSO2001. Therefore, JNJ-77242113 is a promising candidate for further development in systemic, IL-23-driven diseases, such as psoriasis.

To date, JNJ-77242113 has been studied in several Phase 1 and Phase 2 studies. For the most comprehensive nonclinical and additional clinical information regarding JNJ-77242113, refer to the latest version of the Investigator's Brochure (IB) and Addenda for JNJ-77242113.

The term "study intervention" throughout the protocol, refers to study drug as defined in Section 6.1.

The term "sponsor" used throughout this document refers to the entities listed in the Protocol Supplementary Information page(s), which will be provided as a separate document.

### 2.1. Study Rationale

Generalized Pustular Psoriasis (GPP) is rare and represents active, unstable disease. The patient is pyrexial with red, painful, inflamed skin studded with monomorphic, sterile pustules which may coalesce to form sheets. Patients with GPP frequently need to be admitted to the hospital for management. Total or subtotal involvement of the skin by active psoriasis is known as Erythrodermic Psoriasis (EP). Chronic plaque psoriasis may gradually progress as plaques become confluent and extensive. EP may impair the thermoregulatory capacity of the skin, leading to hypothermia, high output cardiac failure, and metabolic changes including hypoalbuminaemia and anaemia due to loss of iron, vitamin B12, and folate (Langley 2005). Multiple therapies have been approved in Japan, however, there are still substantial unmet need for GPP and EP.

Targeting IL-23 is a highly effective approach for treating moderate to severe plaque psoriasis, GPP, and EP. GPP alone is associated with mutations in IL36RN (Sugiura 2014). However, increased expression of IL-36 is correlated with increased expression of cytokines that are known to be involved in the pathogenesis of psoriasis (IL-17A, IL-22, TNF- $\alpha$ , IL-23, and IFN- $\gamma$ , but not IL-12 and IL-17F). The results indicate that the IL-36 cytokines are not only regulated by Th17 cytokines, but that they themselves can regulate the expression and enhance the function of Th17 cytokines (Carrier 2011). IL-23 is composed of a unique p19 subunit coupled with the common

p40 subunit shared with IL-12, and signals through the heterodimeric IL-23 receptor (IL-23R)/IL-12 receptor beta 1 (IL-12R $\beta$ 1) complex (Teng 2015). Binding of IL-23 to the IL-23R complex leads to phosphorylation of STAT3 and IL-23 induced expression of proinflammatory cytokines, such as IL-17A/F and IL-22. Existing highly successful biologic therapies targeting the p19 subunit of IL-23, such as guselkumab (Blauvelt 2017; Reich 2017) and risankizumab (Gordon 2018), act by preventing engagement of this ligand with the IL-23R ultimately causing reduced signaling. In addition, guselkumab and risankizumab have already been approved for the treatment of GPP and EP in Japan (Sano 2018; Yamanaka 2023).

JNJ-77242113 is a 13-amino acid peptide that binds directly to the IL-23R subunit and prevents IL-23, inhibiting proximal IL-23R signaling and downstream effector functions (eg, cytokine secretion). For those patients who prefer oral medication, oral therapies with high efficacy, long-term clinical remission, and good safety profile are more convenient and JNJ-77242113 may meet this unmet need. It has shown encouraging efficacy and safety results in Phase 2b study (77242113PSO2001) in participants with plaque psoriasis.

Based on the positive results observed in the Phase 2 study, JNJ-77242113 is being further assessed in this Phase 3 program. Study 77242113PSO3005 is a Phase 3, open-label, multicenter study to evaluate the efficacy and safety of JNJ-77242113 for the treatment of participants with GPP or EP.

## 2.2. Background

Two Phase 1 studies (PN-235-01 and 77242113PSO1002) in healthy participants have been completed and 1 Phase 1 study (77242113PSO1003) is ongoing in healthy participants. One Phase 2b study of JNJ-77242113 for the treatment of moderate to severe plaque psoriasis (77242113PSO2001) has also been completed and demonstrated a favorable efficacy and safety profile for JNJ-77242113.

## Clinical Studies

### *Efficacy/Safety Studies*

#### Phase 1

Overall, the safety data from 3 Phase 1 studies in healthy participants demonstrate that single and multiple oral doses of JNJ-77242113 administered as an oral solution (PN-235-01, final data) and single oral doses administered as immediate-release (IR) tablets or CCI [REDACTED]

[REDACTED] (77242113PSO1002 in Japanese and Chinese healthy participants, final data and 77242113PSO1003 in non-Japanese healthy participants, preliminary data) were generally well tolerated and with no safety signals.

#### Phase 2

Study 77242113PSO2001, was a Phase 2b multicenter, randomized, double-blind, placebo-controlled, dose-ranging, parallel-group, multicenter study to evaluate the efficacy and safety of JNJ-77242113 treatment in 255 adults with moderate to severe plaque psoriasis over 16 weeks. In

Study 77242113PSO2001, a dose response was observed for the primary endpoint (Psoriasis Area and Severity Index [PASI] 75 response at Week 16). A statistically significant higher proportion of participants in each JNJ-77242113 dose group achieved a PASI 75 response at Week 16 (37.2% for 25 mg once daily, 58.1% for 50 mg once daily, 51.2% for 25 mg twice daily, 65.1% for 100 mg once daily, 78.6% for 100 mg twice daily; nominal  $p=0.002$  for 25 mg once daily; nominal  $p<0.001$  for all other dose groups) than the placebo group (9.3%). All statistical testing was performed at the 2-sided 0.05 significance level.

Secondary endpoints (Investigator Global assessment [IGA] score of cleared [0] or minimal [1], IGA score of cleared [0], PASI 90 score, PASI 100 score and Dermatology Life Quality Index [DLQI] score of 0 or 1) achieved statistical significance at a nominal significance level of 0.05 (2-sided) at Week 16 for all doses compared with placebo. At Week 16, participants in each of the JNJ-77242113 dose groups had a statistically significant greater improvement (reduction) as measured by PASI total score, body surface area (BSA), Psoriasis Symptom and Sign Diary (PSSD) symptom score, and PSSD sign score from baseline than participants treated with placebo.

Safety data are summarized for participants who completed 77242113PSO2001 at the Week 16 visit:

- Overall, there was no clear evidence of a dose-dependent increase in the occurrence of specific adverse events (AEs) across the JNJ-77242113 groups.
- The proportions of participants who experienced 1 or more AEs were similar in the combined JNJ-77242113 (52.4%) and placebo (51.2%) groups.
- The most frequently reported AEs were in the Infections and infestations system organ class (SOC) and were similar between the combined JNJ-77242113 (30.2%) and placebo (27.9%) groups. The most common AEs by preferred term (PT) in this SOC were COVID-19 (10.8% and 11.6%), nasopharyngitis (7.1% and 4.7%), and upper respiratory tract infection (2.4% and 2.3%) in the combined JNJ-77242113 and placebo groups, respectively. In the Gastrointestinal disorders SOC, AEs were reported in 11.3% of participants in the combined JNJ-77242113 group and 11.6% in the placebo group. Other AEs by PT reported by at least 5% of participants included headache and cough.
- The percentage of participants with 1 or more serious adverse events (SAEs) through the end of study was small, with 3 participants (1.4%) experiencing 1 SAE each. All events were singular in nature and deemed not related to study intervention per the investigator.
- The proportion of participants who discontinued study intervention due to 1 or more AEs was small (n=6). Three out of the 6 events were in the Gastrointestinal SOC (n=1 each: abdominal pain, abdominal discomfort, and nausea). The other 3 events included suicide attempt, weight increase, and transaminases increase (n=1 each).
- Rates of abnormal laboratory test result were generally low and comparable between the treatment groups.
- There were no deaths or malignancies reported.

## Human Pharmacokinetics and Immunogenicity

The clinical data available to date supporting the safety, pharmacokinetics (PK) and pharmacodynamics (PD) of JNJ-77242113 are from completed Phase 1 studies in healthy volunteers and Phase 2 studies in adults with moderate to severe plaque psoriasis.

PK data from first-in-human (FIH) study PN-235-01 indicate that systemic exposure ( $C_{max}$  and AUC) to JNJ-77242113 is dose proportional across the dose range evaluated to date. After multiple once daily doses, steady state was achieved by Day 7 (earliest timepoint evaluated), with minimal drug accumulation consistent with the observed mean terminal phase half-life of approximately 9 to 12 hours.

The PK results 77242113PSO1002 indicate that the exposure ( $C_{max}$  and AUC) of JNJ-77242113 increased with dose (100 to 300 mg) in Japanese participants, with no apparent difference in exposure between Japanese and Chinese participants (300 mg). The PK results from this study are also consistent with and comparable to the PK in predominantly white participants in both FIH Study PN-235-01 and the ongoing Study 77242113PSO1003.

The PK results from 77242113PSO1003 indicate that concomitant food (high calorie, high-fat or low calorie, low-fat breakfast) increased the median time to reach  $t_{max}$  and significantly reduced the rate ( $C_{max}$ ) and extent (AUC) of JNJ-77242113 absorption. Based on the food effect data from Protocol 77242113PSO1003, study intervention should be administered under fasted conditions.

Using the population PK model, a number of baseline participant characteristics were evaluated as potential covariates affecting JNJ-77242113 PK parameters. Of the covariates evaluated, only CCI [REDACTED] were found to be significant. Of note, laboratory markers of renal and hepatic function were not found to be significant covariates affecting the PK of JNJ-77242113, consistent with the nonclinical and clinical metabolic clearance and excretion of the drug.

No CCI [REDACTED] have been detected in the completed Phase 1 clinical studies. The overall incidence of CCI [REDACTED] in the Phase 2b study (77242113PSO2001) was low. Given that the peptide is administered by the oral route and does not have an endogenous counterpart, the risk of adverse effects caused by CCI [REDACTED] is expected to be minimal.

Refer to the JNJ-77242113 IB for more information on clinical studies, pharmacokinetic, nonclinical pharmacology, and toxicology.

### 2.3. Benefit-risk Assessment

Detailed information about the known and expected benefits and risks of JNJ-77242113 may be found in the IB. The list provided in Section 2.3.1 describes the potential risks associated with the blockage of IL-23.

### 2.3.1. Risks for Study Participation

Potential Risks of Clinical Significance	Summary of Data/ Rationale for Risk	Mitigation Strategy
Potential Risks Due to Study Intervention JNJ-77242113		
Hypersensitivity reactions	Exogenous peptides administered orally or systemically have the potential to cause hypersensitivity reactions.	
 
This potential risk will be explained in the informed consent form (ICF) and participants will be trained to recognize early signs of impending anaphylaxis (Sampson 2006) and seek medical attention.
 
Participants with known allergy, hypersensitivity, or intolerance to JNJ-77242113 or its excipients will be excluded from the study.
 
Any participant who develops a serious hypersensitivity reaction such as anaphylaxis must discontinue study intervention (Section 7).
 

ADA production	Exogenous peptides administered orally or systemically have the potential to induce anti-drug antibodies (ADA) production, which may mediate untoward reactions such as reduced efficacy or hypersensitivity.	
 
This potential risk will be explained in the ICF and evaluated by measuring ADA and pharmacokinetics (PK) for analysis.
 
Participants are encouraged to consistently take their study intervention 24 hours apart, as directed.
 

Infection	Clinical experience with marketed IL-23 pathway blockers includes precautions for infections and tuberculosis (TB).	
 
This potential risk will be explained in the ICF.
 
Participants with evidence of active TB will be excluded from the study (Section 5.2).
 
Participants must agree not to receive a live viral or live bacterial vaccination 4 weeks prior to enrollment in the study or during the study and for 4 weeks after receiving the last dose of study intervention (Section 5.2). Additional guidance is provided for the BCG vaccine in Section 5.2.
 
Participants will be educated and instructed to seek medical attention if they develop signs or symptoms suggestive of an infection, and investigators are instructed to monitor for signs or symptoms of infections, including TB (Section 8.3.7).
 
Discontinuation of a participant's study intervention must be strongly considered if the participant develops a serious infection,
 

Potential Risks of Clinical Significance	Summary of Data/ Rationale for Risk	Mitigation Strategy
		including but not limited to sepsis or pneumonia. In addition, any serious infection should be discussed with the medical monitor or designee, and study intervention should be withheld until the clinical assessment is complete (Section 7).

### 2.3.2. Benefits for Study Participation

JNJ-77242113 has demonstrated significant efficacy compared with placebo for ClinROs and PROs including disease severity and extent, quality of life measures, and participant-reported signs and symptoms of psoriasis based on Phase 2b Study 77242113PSO2001 (Section 2.2). Participants with GPP and EP may benefit from receiving JNJ-77242113 and receiving routine clinical care during this study.

### 2.3.3. Benefit-risk Assessment for Study Participation

Taking into account the measures taken to minimize risk to participants of this study, the potential risks identified in association with JNJ-77242113 are justified by the anticipated benefits that may be afforded to participants with GPP and EP.

## 3. OBJECTIVES, ENDPOINTS, AND ESTIMANDS

Objectives	Endpoints
Primary	
 
To evaluate the efficacy of JNJ-77242113 in participants with GPP or EP
 
Proportion of participants with GPP who experience treatment success (based on Clinical Global Impression CGI scale according to Japanese Dermatological Association [JDA] total score) at Week 16.
 
Proportion of participants with EP who experience treatment success (based on CGI scale) at Week 16.
 

Secondary	
 
To further evaluate the efficacy of JNJ-77242113 in participants with GPP or EP
 
Proportion of participants with GPP or EP who experience treatment success (for GPP: based on CGI scale according to JDA total score and for EP: based on CGI scale) over time.
 
Change from baseline in the total score of the JDA severity index for GPP over time.
 
Change in baseline in severity classification (mild, moderate, severe) of the JDA severity
 

Objectives	Endpoints
	
index for GPP over time.
 
 
Change from baseline in body surface area (BSA) of involvement of lesion for EP over time.
 
Proportion of participants who achieve an Investigator's Global Assessment (IGA) score of cleared (0) or minimal (1) over time.
 
Proportion of participants who achieve an IGA score of cleared (0) over time.
 
Percent improvement from baseline in Psoriasis Area and Severity Index (PASI) over time.
 

 
To evaluate the effect of JNJ-77242113 treatment on health-related quality of life (HRQoL) in participants with GPP or EP
 
	
 
Change from baseline in Dermatology Life Quality Index (DLQI) score over time.
 
Proportion of participants who achieve a DLQI score of 0 or 1 over time.
 
Change from baseline in EQ-5D-5L (domain scores and visual analog scale [VAS]) over time.
 

 
To assess the safety and tolerability of JNJ-77242113 in participants with GPP or EP
 
	
 
Frequency and type of AEs and SAEs.
 

Exploratory	

 
To further explore the efficacy of JNJ-77242113 in participants with GPP
 
	
 
Change from baseline in components (skin symptoms, systemic symptoms/laboratory findings) of the JDA severity index for GPP over time.
 

 
To further evaluate the effect of JNJ-77242113 on HRQoL in adolescent participants with GPP or EP
 
	
 
Change from baseline in Children's DLQI (CDLQI) over time.
 
Change from baseline in Children's DLQI (CDLQI) score 0 or 1 over time.
 

 
To evaluate the PK and immunogenicity of JNJ-77242113
 
	
 
JNJ-77242113 PK parameters.
 
Incidence of anti-drug antibodies to JNJ-77242113.
 

 
To explore biomarkers in participants with GPP or EP
 
	
 
Change from baseline in levels of blood biomarkers.
 

## ESTIMANDS

The primary estimand (ie, a precise definition of the primary targeted treatment effect) is defined for GPP and EP, respectively by the following 5 attributes:

**Study Intervention:**

Experimental: JNJ-77242113

**Population:**

- Participants  $\geq 12$  years of age with GPP
- Participants  $\geq 12$  years of age with EP

**Variable:**

Binary response variables for the primary endpoints:

- Treatment success for GPP: a responder (participant with treatment success defined as at least "Minimally Improved" rating in CGI scale for GPP according to JDA total score) at Week 16.
- Treatment success for EP: a responder (participant with treatment success defined as at least "Minimally Improved" rating in CGI scale for EP) at Week 16.

**Intercurrent Event (ICE):**

Intercurrent event	Corresponding Strategy
Discontinuation of study intervention for any reason prior to Week 16.	Treatment Policy: observed data will be used regardless of whether or not this ICE had occurred.

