### 6.9.1. Prohibited Therapy

All experimental therapies or new investigational interventions (except for JNJ-77242113), including therapies for psoriasis or other conditions, must be discontinued prior to the first dose administration of study intervention per Exclusion Criteria (Section 5.2) and remain prohibited during the study (until ET Visit for participants who terminate early or until last study intervention administration visit). For guidance regarding the COVID-19 vaccine see Section 6.9.1.3.

The sponsor's medical monitor must be notified in advance (or as soon as possible thereafter) of any instances in which prohibited therapies are administered. The participant may be required to discontinue study intervention (Section 7.1.3).

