### **Phototherapy or Systemic Therapy**

The use of phototherapy or systemic medications (other than MTX, retinoid, and cyclosporine) that could affect psoriasis or the efficacy evaluation, is not permitted at any time during the study (until ET Visit for participants who terminate early or until last study intervention administration visit).

These medications include, but are not limited to,

- those targeted for reducing TNF $\alpha$  (including but not limited to infliximab, etanercept, or adalimumab).
- drugs targeted for reducing IL-12/23, IL-17, IL-23, IL-36 (including but not limited to ustekinumab, guselkumab, tildrakizumab, secukinumab, risankizumab, ixekizumab, brodalumab, or spesolimab).
- alpha-4 integrin antagonists (including but not limited to natalizumab).
- JAK inhibitors (including but not limited to tyrosine kinase 2 inhibitors).
- PDE4 inhibitors (including but not limited to apremilast).
- oral and injectable (IV, intramuscular, or intralesional) corticosteroids.
- any other conventional systemic therapies that could affect psoriasis or the efficacy evaluation.
- antimarial agents.
- herbal treatments.
- traditional Taiwanese, Korean, or Chinese medicines.

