### **MTX, Retinoids, or Cyclosporine for Treatment of Psoriasis**

In case of receiving retinoids, 2 weeks with stable dose before the first administration of study intervention is necessary, and any change in the dose should be avoided through Week 52. Dose can be reduced; however, it cannot be re-escalated once it is reduced. After Week 52, there is no limitation on retinoid.

In case of receiving MTX (<20 mg/week) or cyclosporine ( $\leq$ 5 mg/kg/day) at screening, at least 2 weeks with stable dose before the first administration of study intervention is necessary and this stable dose should continue through Week 16. In case of participants with confirmed clinical improvement, dose reduction is allowed before Week 16, but dose cannot be re-escalated. After Week 16, cyclosporine should be tapered off and discontinued by Week 32. If the condition of a participant worsens after tapering cyclosporine, the investigators should consider discontinuation of study drug and pursue alternative treatment options. After Week 16, MTX should be tapered off and an attempt should be made to discontinue MTX by Week 32. Minimal dose of MTX should

be maintained throughout the study if the participant is not able to discontinue MTX completely. Participants are not permitted to receive both MTX and cyclosporine at the same time during the study.

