### **7. DISCONTINUATION OF STUDY INTERVENTION AND PARTICIPANT DISCONTINUATION/WITHDRAWAL**

#### **7.1. Discontinuation of Study Intervention**

If a participant discontinues study intervention for any reason before the end of the study, then the ET Visit assessments must be obtained (Section 1.3) as soon as possible. Study intervention assigned to the participant who discontinued study intervention may not be assigned to another participant (Section 6.2). Additional participants will not be entered in this study. Participants who discontinue study intervention but do not terminate study participation will continue to return for protocol specified procedures and evaluations. Discontinuation from study intervention does not mean that the participant is required to withdraw informed consent and leave the study.

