### 7.1.3. Permanent Discontinuation of Study Intervention

A participant's study intervention must be permanently discontinued if:

- The participant withdraws consent or assent to receive study intervention.
- The investigator believes that for safety reasons or tolerability reasons (eg, AE) it is in the best interest of the participant to discontinue study intervention.
- Participant meets the Sampson criteria for anaphylaxis ([Sampson 2006](#)) following study intervention administration.
- The participant becomes pregnant or plans a pregnancy during the study period. Refer to [Appendix 4: Contraceptive and Barrier Guidance](#).
- Participant initiates protocol-prohibited medications, treatments, or interventions (outlined in Section [6.9](#)) that have an impact on psoriasis efficacy evaluations at the discretion of the medical monitor.
- Participant develops a malignancy including squamous cell skin cancer. Consideration may be given to allow participants, who develop  $\leq 2$  basal cell skin cancers and who are adequately treated with no evidence of residual disease, to continue to receive study intervention.
- The participant develops a systemic opportunistic infection during the study period.
- Participant develops a recurrent or chronic serious infection during the study period.
- The participant is deemed ineligible according to the following TB screening criteria:
  - A diagnosis of active TB is made.

- A participant has symptoms suggestive of active TB based on follow-up assessment questions and/or physical examination or has had recent close contact with a person with active TB and cannot or will not continue to undergo additional evaluation.
- A participant undergoing evaluation has a chest radiograph with evidence of current active TB and/or a positive IGRA result, unless active TB can be ruled out and appropriate treatment for latent TB can be initiated prior to the next administration of study intervention and continued to completion. Indeterminate IGRA results should be handled as in Section 8.3.7. Participants with persistently indeterminate IGRA results may continue without treatment for latent TB if active TB is ruled out, their chest radiograph (both posterior-anterior and lateral views, substitutable with chest CT) shows no abnormality suggestive of TB (active or old, inactive TB) and the participant has no additional risk factors for TB as determined by the investigator and medical monitor.

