## Primary Endpoint Analyses

For the primary endpoint analyses, data from full analysis set (FAS) which is the population of participants who received at least 1 dose of study intervention will be analyzed. The number, proportion of participants with treatment success, and 95% Clopper-Pearson exact confidence interval (CI) will be provided for GPP and EP groups.

The primary endpoints will be analyzed using the primary estimand.

After accounting for the ICE for the primary estimand, participants with missing data for the primary endpoints at Week 16 will be considered as non-responders.

The detailed methods of analysis and the data-handling rules for primary endpoints will be described in the SAP.

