4.2.2. Estimands

4.2.2.1. Primary Estimand

The primary estimand (ie, a precise definition of the primary targeted treatment effect) is defined for GPP and EP, respectively by the following 5 attributes:

Study Intervention:

- Experimental: JNJ-77242113

Population:

- Patients \geq 12 years of age with GPP
- Patients \geq 12 years of age with EP

Variable:

Binary response variables for the primary endpoints:

- Treatment success for GPP: a responder (participant with treatment success defined as at least "Minimally Improved" rating in CGI scale for GPP according to the JDA total score) at Week 16.
- Treatment success for EP: a responder (participant with treatment success defined as at least "Minimally Improved" rating in CGI scale for EP) at Week 16.

Intercurrent Events (ICE) and Their Corresponding Strategies:

Intercurrent Event	Strategy	Description
Discontinuation of study intervention for any reason on or prior to Week 16.	Treatment-policy	Observed data will be used regardless of whether or not this ICE had occurred.

Summary Measure (Population-level Summary):

- Proportion of participants with GPP who experience treatment success at Week 16.
- Proportion of participants with EP who experience treatment success at Week 16.

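### The primary estimand does not address starting other GPP/EP therapy by Week 16, so an improved rating on such therapy counts as a drug success; the SAP's supplementary estimand catches most of these cases but not all

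*Protocol*

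**What the plan says.** Protocol Sections 3 and 9.3.2 and SAP 4.2.2.1 define the primary estimand with a single intercurrent event, stopping study intervention by Week 16. The strategy is treatment policy. The protocol puts it as "Treatment Policy: observed data will be used regardless of whether or not this ICE had occurred" and the SAP as "Observed data will be used regardless of whether or not this ICE had occurred". Non-response is imposed only where the rating is absent: "participants with missing data for the primary endpoints at Week 16 will be considered as non-responders".

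Four provisions determine who can have a Week 16 rating after other therapy:

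- Protocol 7.1: "Participants who discontinue study intervention but do not terminate study participation will continue to return for protocol specified procedures and evaluations".
- Protocol 6.9.1.1, on phototherapy and systemic therapy other than methotrexate, retinoid and cyclosporine: use "is not permitted at any time during the study (until ET Visit for participants who terminate early". The ban therefore lapses at the Early Termination (ET) Visit.
- Protocol 6.9.1, on someone given prohibited therapy: "The participant may be required to discontinue study intervention". Protocol 7.1.3 makes permanent discontinuation the default for prohibited treatments "that have an impact on psoriasis efficacy evaluations at the discretion of the medical monitor".
- Protocol 6.9.1.1, on background methotrexate or cyclosporine: "this stable dose should continue through Week 16". Retinoid dose changes are to be avoided through Week 52.

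SAP 4.2.2.2 adds a supplementary estimand, which the protocol does not contain. It scores as non-response both stopping study intervention (ICE 1) and starting other therapy that could improve GPP/EP, unless the protocol allows it (ICE 2). SAP 4.2.3.2 applies the same proportion and exact interval. SAP Appendix 8 lists the therapies, and item 2 of that list leaves out methotrexate, retinoid and cyclosporine by name, without conditions.

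**The concern.** The hypothesis attributes efficacy to this drug, and the evidence for it is one proportion per disease group. In a randomised comparison, treatment policy would apply to both arms and the contrast would keep a clear meaning. Here there is one arm, so a success reached on another therapy can only raise the reported proportion. The bar is low (at least minimally improved against Week 0), and Protocol 2.1 says that two IL-23 biologics are already approved for both conditions in Japan. An effective alternative started before Week 16 could plausibly clear that bar. With 8 participants per group, a single case moves the headline visibly.

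**Working it through.** **Step 1: who is affected.** The scoring follows from the estimand tables, the missing-data rule, the Schedule of Activities and Appendix 8.

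| Course up to Week 16 | Week 16 CGI | Primary | Supplementary |
|---|---|---|---|
| Stops drug; ET Visit and 4-week safety follow-up only | None | Non-response | Non-response |
| Stops drug, keeps attending, starts other therapy | Observed | As rated | Non-response (ICE 1) |
| Stays on drug, starts a therapy listed in Appendix 8 | Observed | As rated | Non-response (ICE 2) |
| Stays on drug, starts or increases methotrexate, retinoid or cyclosporine | Observed | As rated | As rated, on the list as written |

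In the first row, CGI is scheduled at the ET Visit but not at the safety follow-up. SAP 4.1.1 uses nominal visits, so an ET rating would not ordinarily stand in for Week 16. The second and third rows are where the two analyses can differ. The fourth escapes both.

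**Step 2: size per participant.** The plan has no power or precision figure to reproduce: the sample size is set on feasibility (8 + 8 = 16). With n = 8 per group, one participant is 1/8 = 12.5 points. The planned interval is two-sided 95% Clopper-Pearson, for x successes:

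- lower limit = 2.5% quantile of Beta(x, n − x + 1)
- upper limit = 97.5% quantile of Beta(x + 1, n − x), or 100% if x = n

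| x/8 | Proportion | 95% CI |
|---|---|---|
| 4 | 50.0% | 15.7% to 84.3% |
| 5 | 62.5% | 24.5% to 91.5% |
| 6 | 75.0% | 34.9% to 96.8% |
| 7 | 87.5% | 47.3% to 99.7% |
| 8 | 100% | 63.1% to 100% |

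Check at 8/8: the lower limit is 0.025^(1/8) = 0.631.

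One extra success lifts the lower limit by 8.8 points from 4 to 5, 12.4 points from 6 to 7, and 15.7 points from 7 to 8 (from unrounded limits).

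**Step 3: direction and frequency.** The composite can turn a success into a non-response but never the reverse. The primary count is therefore never below the supplementary count, and k discordant participants in a group of 8 separate the two by 12.5 × k points. Neither document gives a rate of starting other therapy, so k cannot be predicted. At k = 0 the two analyses agree.

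**The case against.** The best defence is that the sponsor foresaw the event. SAP 4.2.2.2 scores it as non-response with the same interval, version 2 of the SAP clarified ICE 2 and added Appendix 8, and SAP Appendix 5 lists users of such therapy and all concomitant medication. With 8 per group, no case will stay hidden. Treatment policy is a recognised strategy, and the primary is overstated only relative to a different estimand. Some affected participants may also have improved on study drug before the other therapy began. All of this stands, and it limits the seriousness of the point.

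It does not remove the point. The supplementary estimand merges stopping drug with other therapy, so a gap between the two results cannot be assigned to either cause without a count. Neither document says why treatment policy suits a single-arm study.

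On the three exempted drugs, ICE 2 could be read to catch a new start or an increase, because it spares only what the protocol allows and the protocol calls for stable dosing. But ICE 2 speaks of initiation, not increase, and the list that defines it removes the drugs by name. The wording needs settling.

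A reader might also infer three stronger things that the documents do not support:

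- That everyone who stops and switches is counted as a success. Those who follow only the ET and safety follow-up path are already non-responders.
- That prohibited therapy on study drug is freely tolerated. Discontinuation is the default, subject to the medical monitor's discretion.
- That an expected inflation can be calculated. No rate is given from which to do so.

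**Conclusion.** The gap in the primary estimand is real but narrow. It affects participants who start other GPP/EP therapy by Week 16, have an observed Week 16 rating, and are rated at least minimally improved. They are either still attending after stopping drug or still on drug at the medical monitor's discretion. Each adds 12.5 points to a group of 8, assuming the target of 8 is met and that improvement after other therapy should not be credited to the study drug. The total effect is unknown and may be nil.

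It would be wrong to infer a risk of a false-positive decision: SAP Section 2 plans no formal test and the plan sets no success threshold. The harm is a possibly overstated headline proportion and interval, most of which the supplementary analysis would expose. What neither analysis exposes, on the list as written, is a start or increase of methotrexate, retinoid or cyclosporine by someone still on study drug.

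**What to change.** 1. **Close the gap in the list.** For scoring only, limit the exclusion in SAP Appendix 8 item 2 to background use of the three drugs that is present at Week 0 and not increased. Word ICE 2 to cover both initiation and increase of them. This changes no rule on what participants may take.
2. **Preferred, if it can be done by amendment before the relevant database lock.** Add the corrected ICE 2 to the primary estimand in Protocol 3 and 9.3.2 and SAP 4.2.2.1, with the composite (non-responder) strategy. State that Appendix 8 therapies started after the ET Visit count, since the ban has then lapsed and they might otherwise be read as allowed. Keep treatment policy for stopping drug without other therapy.
3. **Otherwise, leave the primary unchanged.** Show the supplementary composite beside it in the same table with exact intervals. Report how many discordant participants took other therapy and how many only stopped study drug.

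Cost: item 1 needs a SAP revision, and item 2 also needs a protocol amendment. SAP version 2 is dated 4 April 2025, so a late change to the primary estimand of an open-label study may be criticised as post hoc, and the reported rate may fall by 12.5 points per affected participant. Item 3 needs only a table layout and a count. Concomitant therapy is already recorded at every visit, so no new type of assessment is needed, but the sponsor should confirm that the case report form captures dose increases of the three drugs.
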